The goal of this study is to develop a method for establishing a reproducible and controlled Cryptosporidium infection in healthy adults that temporarily results in symptoms of cryptosporidiosis and is expected to resolve naturally within approximately 7-21 days. A healthy volunteer CHIM study is expected to allow for a careful, early examination of the pharmacokinetic-pharmacodynamic (PK-PD) relationship of a future investigational drug in a controlled setting, providing valuable data that informs future trial designs (Darton et al 2015, Pollard et al 2012). In contrast to real-world settings, participants in a cryptosporidiosis CHIM will have diarrhea due to a single pathogen, not potentially multiple ones. This will allow for unbiased interrogation of the effect of an investigational drug on clinical and parasitological endpoints. The safety and feasibility of controlled human Cryptosporidium parvum studies are well documented the literature (Chappell et al 2006, DuPont et al 1995, Okhuysen et al 1999). If successful, this CHIM methodology would be used in the future (with different study participants) to enable assessment of novel therapies and vaccines for the treatment and prevention of cryptosporidiosis. A Cryptosporidium CHIM will provide important data demonstrating the prospect of benefit and informing dose selection of new therapies and vaccines before they are tested in vulnerable pediatric populations.

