Outpatient follow-up period: After the domicile period, participants will be followed on an outpatient basis ending on Day 56 following the ABO809 administration. Infection is expected to be self-limiting in healthy adults and resolve by Day 21. Published literature on the intensity of infection and oocyst excretion patterns of *C. parvum* in healthy volunteers suggests that oocyst excretion is limited to the first 14 days in up to 86% participants with diarrhea, and excretion prolonged beyond 28 days is observed in only 5% of participants (Chappell et al 1996). Participants will return for follow-up visits on Day 14, 17, 21, 24 and 28 for physical examination and/or to provide collected stool samples (for measurement of oocyst shedding) (see Table 8-1). Safety Follow-Up Calls will be conducted with participants up to Day 56 to collect adverse events that are considered related to administration with ABO809 (see Section 10.1.1.1). Any participants who experience diarrheal symptoms between Day 28 and Day 56 may provide a stool sample for analysis and may return to the study site for an unscheduled visit to consult with the Investigator.

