6.2.3 Rescue medication

To minimize the risk of severe clinical illness, long-term asymptomatic shedding and recurrence of *Cryptosporidium* infection, nitazoxanide may be administered at 500 mg by mouth every 12 hours with food for 3 days as per the U.S. Prescribing Information, under the clinical conditions outlined below. Nitazoxanide is the standard of care for the treatment of cryptosporidiosis. In double-blind, controlled trials in adults and adolescents with diarrhea and with or without enteric symptoms caused by *C. parvum*, nitazoxanide administered at 500 mg BID for 3 days resulted in a 96% clinical response rate 4 to 7 days following the end of treatment. In this study, clinical response was defined as "no symptoms, no watery stools and no more than 2 soft stools within the past 24 hours" or "no symptoms and no unformed stools within the past 48 hours" (Romark 2017).

All participants who receive ABO809 and develop an infection (i.e. oocyst shedding after Day 3), will receive nitazoxanide on Day 21 or as soon as EIA analysis

of Day 17 sample becomes available whether or not they develop clinical symptoms. There are conditions under which participants may receive nitazoxanide earlier: (i) participants with diarrhea persisting until Day 10 will start nitazoxanide on Day 10, (ii) participants with severe diarrheal illness (≥ Grade 3 as per Toxicity Grading Scale for Healthy Adult and Adolescent Volunteers Enrolled in Preventive Vaccine Clinical Trials (2007)) may receive

nitazoxanide unless deemed contraindicated by the Investigator irrespective of timing. Whenever nitazoxanide treatment is administered to participants experiencing clinical symptoms, participants may be domiciled at the discretion of the Investigator until free of clinical symptoms for ≥ 24 hours.

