	Commercially Confidential Informat	tion	
Occult Blood			
Cryptosporidium Antigen by EIA ^{10, 12}			

Period	Post-Study Follow-Up		
Visit Name	Post-Study Follow-Up Call		
Days	6 Month Phone Contact Commercially Confidential Information	12 Month Phone Contact on	
lgA			
	Commercially Confidential Informa	tion	
Evaluation of Clinical Signs and Symptoms ⁶			
CHIM Diary			
Standard of Care Drug Administration (Nitazoxanide) ⁸			
Concomitant medications			
Adverse Events	S ¹⁵	S ¹⁵	
•	Commercially Confidential Information	on	
Safety Follow-Up Call for Study Participants	S	s	
Study completion information			

Commercially Confidential Information

² Serum pregnancy tests at Screening and Day 28. Urine pregnancy test at Baseline.

³ Before ABO809 administration.

⁴ Participants should make every attempt to bring self-collected stool specimen to the clinic for each Outpatient Follow-Up visit. In the 24 hours prior to each Outpatient Follow-Up visit, all stools should be collected.

⁵ During screening, the first diarrheal stool, and the first diarrheal stool with relapse after clinical clearance will be tested for enteral pathogenic micro-organisms.

⁶ Includes number and frequency of diarrheal episodes, stool weight, volume, and grading (see Section 8.3.2, Section 8.4.1, and Appendix 1). Additionally, includes evaluation of nausea, vomiting, abdominal pain or discomfort, abdominal tenderness, abdominal rebound, abdominal distension, fecal urgency, diarrhea, flatulence, tenesmus, poor appetite, dehydration, fever, and electrolyte imbalance

⁸ Nitazoxanide to be administered per Prescribing Information (i.e. 500 mg every 12 hours for 3 days). Nitazoxanide administration will be captured on the standard concomitant medication page, and no specific CRF is required.

Page **50** of **81** Protocol No. CABO809A02101

Period	Post-Study Follow-Up	
Visit Name	Post-Study Follow-Up Call	
Days	6 Month Phone Contact	12 Month Phone Contact

¹¹ Additional tests can be done at the discretion of the Investigator e.g., in the case of dehydration.

Commercially Confidential Information

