2.1.1 General definitions

Study treatment: ABO809, $3x10^6$ *C. parvum* oocysts(CE)/3 mL as concentration for oral suspension. There will be no control drug used in this study. Additional study treatment is nitazoxanide 500 mg as tablet for oral use, which will be used as rescue medication on Day 21 and may be administered earlier based on clinical findings. Both are referred to as study treatment and rescue medication in the document, respectively.

The treatment group name alone (pooled analyses) and in addition to cohort number will be used in statistical analyses and outputs. The following abbreviated treatment groups will be used as the headers in the CSR outputs:

- ABO809 1x10⁴ CE cohort X
- ABO809 1x10⁶ CE cohort Y, if applicable
- ABO809 1x10^x CE cohort Z, if applicable (e.g. alternative dose)

Baseline: The last measurement made prior to administration of the first dose of study treatment. Note this may include measurements taken on the day before single dose administration (e.g. lab tests, ECG, vital signs, etc.).

Study day: Study day will be calculated with respect to the first dose of study treatment. The first day of administration of study treatment (first dose) is defined as Day 1. Day -1 will be the day before Day 1. There is no Day 0 designated in this study.

For assessments collected on or after Day 1, study day = date of assessment - date of first dose of study treatment + 1.

For assessments collected prior to Day 1, study day = date of assessment - date of first dose of study treatment.

Date of administration of study treatment: the day of administration of study treatment (ABO809 dose), is defined as Day 1.

Inpatient Follow-Up period: All participants, whether or not they are symptomatic, will be domiciled at the study site until completion of Day 10 assessments and then discharged if diarrheal symptoms have been resolved for ≥24 hours. Participants who experience symptoms

will remain domiciled for the duration of the diarrheal illness up to Day 21. If a participant experiences diarrhea after Day 10 (after the participant has been discharged from the study site), the participant may be readmitted, at the discretion of the Investigator, to remain domiciled until the cessation of symptoms or Day 21, whichever is earlier.

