Cryptosporidium infection: is defined as the presence of oocysts in at least 1 stool sample starting 72 hours following the administration of ABO809 (or sooner if associated with symptoms suggestive of diarrheal illness), up to Day 10 or Day 28 (separately). If clinical symptoms associated with cryptosporidiosis occur earlier than 72 hours post-administration, then stool samples after the onset of symptoms can be collected for parasitological evaluation. Oocysts will be detected by a commercially available diagnostic EIA test and confirmed by a DFA test if the EIA is positive. The tests will be performed at a Clinical Laboratory Improvement Amendments (CLIA) certified laboratory. Samples that test negative for Cryptosporidium by EIA will be reported as negative for Cryptosporidium without confirmation by DFA.

Resolution of *Cryptosporidium* **infection:** A *Cryptosporidium* infection will be considered resolved when no evidence of *Cryptosporidium* is detected in stool samples collected over ≥ 2 consecutive days. Please refer to the definition of "Number of days to resolution of Cryptosporidium infection" for further details.

Number of days to Cryptosporidium infection onset: is defined as the first occurrence of positive EIA test if it is at/after 72 hours post-challenge, otherwise as the first occurrence of positive EIA test with clinical diarrhea symptoms (if earlier than 72 hours), minus the date of dosing.

Number of days of Cryptosporidium infection: is defined as all days that have at least 1 positive EIA test.

Number of days to resolution of Cryptosporidium infection: is defined as:

- 48 hours after the last occurrence of positive EIA test during the inpatient period following the initial admission into the unit or,
- 48 hours after the last occurrence of positive EIA test during the inpatient period following the readmission into the unit or during the outpatient period up to Day 20 (without clinical diarrhea symptoms and before the start of NTZ) or,
- if there is a clinical relapse during the outpatient period, 48 hours after the last occurrence of positive EIA test with GP60 result showing recrudescence or,
- if clinical relapse during the outpatient period with GP60 result showing reinfection, 48 hours after the last occurrence of positive EIA test before onset of clinical symptoms,

i.e., the last positive EIA test date minus the dosing date +3.

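### For asymptomatic outpatients, SAP 2.1.1.1 stops the last-positive search at Day 20, so an untreated positive stool dated Day 21 can be left out and infection counted as resolved before rescue

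*Protocol*

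**What the plan says.** **Sampling.** Protocol Table 8-1 schedules stool collection and EIA at the outpatient visits on Days 14, 17, 21, 24 and 28. Footnote 4 adds: "In the 24 hours prior to each Outpatient Follow-Up visit, all stools should be collected".

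**Treatment.** Table 8-1 places nitazoxanide at the Day 21 visit. Protocol 6.2.3 says that infected participants "will receive nitazoxanide on Day 21 or as soon as EIA analysis" of the Day 17 sample is available; SAP 2.3.4 repeats this.

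**Resolution.** SAP 2.1.1.1 first gives a general definition: stools free of the parasite over two or more successive days. It then sends the reader to the day-count definition for detail. There, the bullet for outpatients without relapse takes the last positive EIA "during the outpatient period up to Day 20 (without clinical diarrhea symptoms and before the start of NTZ". Later positives enter only "if there is a clinical relapse during the outpatient period", and then only with a GP60 genotyping result. The closing line gives the arithmetic as "the last positive EIA test date minus the dosing date +3" and states no day limit.

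**Analysis.** Time to resolution of infection is a secondary endpoint. SAP 2.5.2 summarises it by Kaplan-Meier, and SAP 2.5.3 censors anyone who takes rescue medication before the event.

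**The concern.** The requirement that the sample precede nitazoxanide already removes treated stools. For a participant who starts nitazoxanide at the Day 21 visit, all that the extra Day 20 limit removes is untreated stools dated Day 21. These can be the last evidence of whether the infection had cleared without drug.

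Protocol 1.1 describes an infection that "is expected to resolve naturally within approximately 7-21 days". The resolution curve is where a reader will look to see whether the model behaves that way. If a participant is still shedding when rescue starts but is counted as resolved some days before, the curve looks more complete than the data are. The error runs in one direction only, towards earlier and more frequent natural resolution.

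**Working it through.** The plan states no figure to reproduce, so the check applies the SAP rule to the scheduled stool days.

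**Inputs**
- Origin of the time scale: "The first day of administration of study treatment (first dose) is defined as Day 1" (SAP 2.1.1).
- Formula and Day 20 limit: SAP 2.1.1.1.
- Outpatient stool visits: Days 14, 17, 21, 24, 28 (SAP 2.1.1, Protocol 3.3).
- Rescue: Day 21, or earlier on the Day 17 result (Protocol 6.2.3).
- Censoring: rescue before the event (SAP 2.5.3).

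**Step 1: the value.** With the last admitted positive on Day d, the value is (d − 1) + 3 = d + 2.

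| Last positive admitted | Value | Shortfall against Day 21 | Status if rescue is on Day 21 |
|---|---|---|---|
| Day 10 | 9 + 3 = 12 | 11 | event |
| Day 14 | 13 + 3 = 16 | 7 | event |
| Day 17 | 16 + 3 = 19 | 4 | event |
| Day 20 | 19 + 3 = 22 | 1 | censored |
| Day 21 | 20 + 3 = 23 | 0 | censored |

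The status does not depend on whether rescue is placed at 21 (study day) or 20 (days since dosing): 19 lies below both, and 22 and 23 lie above both.

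**Step 2: the affected case.** A participant without symptoms is positive on Days 17 and 21, has no positive dated Day 20, and starts nitazoxanide at the Day 21 visit. The SAP value is 19, an event, although the next scheduled stool is positive. With the Day 21 stool admitted the value is 23 and the participant is censored. If the pattern is positive on Day 14, negative on Day 17 and positive on Day 21, the values are 16 and 23.

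**Step 3: cases that are not affected**
- The 24-hour window can yield a stool dated Day 20. If it is positive, the value is 22 and the participant is censored.
- If nitazoxanide starts on Day 18 or 19 after the Day 17 result, a value of 19 is not before rescue. The participant is censored, and the Day 21 stool is not pre-treatment.
- With no positive by Day 20 the value is undefined, not early.

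**Step 4: rough ceiling on numbers.** Protocol 12.8.1 assumes 90% infection, so 0.90 × 30 = 27 infected. Protocol 4.1 cites shedding confined to 14 days in up to 86% of participants with diarrhea, and says that "excretion prolonged beyond 28 days is observed in only 5% of participants". Taking 5% to 14% as still shedding around Day 21 gives 27 × 0.05 = 1.35 to 27 × 0.14 = 3.78. With 60 dosed, 54 × 0.05 = 2.7 to 54 × 0.14 = 7.56.

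**Step 5: effect on the curve.** As an illustration, let 27 be infected, k of them affected with a value of 19, and all others have a value of 16. Under the Day 20 limit the Kaplan-Meier share unresolved at 20 is 0%. If the k participants are censored at rescue instead, it is k/27: 3.7%, 7.4% and 14.8% for k = 1, 2 and 4. The median is 16 either way.

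**The case against.** The strongest reply is that the general definition blocks the false event. A participant positive on Days 17 and 21 has no scheduled run of negative days in between, so the two definitions read together would give no resolution, and censoring at rescue. This does not rescue the rule, because the general definition refers the reader to the day-count definition, and that is where the Day 20 limit sits. What stands is that two programmers could reasonably code this differently.

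Other points stand and narrow the issue:
- A reader might infer that no asymptomatic outpatient can have a late untreated positive counted. That is too broad: positives dated Day 20 are inside the limit.
- A reader might infer that the Day 21 result is lost to the trial. It is not. It still enters the by-visit EIA tables and listings (SAP 2.4.2), the count of positive days and the Day 28 infection endpoint. One derived variable is affected.
- The closing formula does not contradict the bullets. It can be read as their arithmetic, although its silence on the limit invites a different reading.
- Nitazoxanide is captured on the standard concomitant medication page, and no visible text says that a clock time is recorded. Without times, Day 20 is a cautious last day before scheduled rescue.
- Footnotes 10 and 12 to the stool and EIA rows are not visible in the public text and may bear on outpatient sampling.

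**Conclusion.** The point holds within limits. The Day 20 restriction can turn a participant who should be censored at nitazoxanide into an observed resolution at 19, 16 or 12. This requires that the participant has no symptoms, starts nitazoxanide at the Day 21 visit, has a positive stool dated Day 21 and none dated Day 20, and has an earlier positive. The SAP does not say whether the EIA test date is the collection date or the visit date. If it is the visit date, stools passed on Day 20 would also fall outside the limit.

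The number affected cannot be estimated from the documents. It is tempting to read 1 to 4 of 27 as an estimate, or to say that all would appear resolved when the true share is 86% to 95%. The documents do not support either. The cited shedding figures concern participants with diarrhea, the 86% is itself given as a maximum, and the count takes in everyone still shedding rather than those who meet all the conditions above. It serves only as a rough ceiling.

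The primary endpoint, which ends at Day 10, is untouched. The effect is on event status and the upper tail of a descriptive secondary curve. It is worth correcting because the change is small and the bias has a known direction.

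**What to change.** In the day-count definition in SAP 2.1.1.1:

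1. Replace the Day 20 limit and the nitazoxanide condition with a single rule: use the last positive EIA in any stool collected before the first nitazoxanide dose, including the specimen brought to the Day 21 visit when nitazoxanide starts at that visit.
2. Base the rule on stool collection date, and on time where it is recorded. State what is done when only dates are available.
3. Censor at the first nitazoxanide dose any participant whose last stool before that dose is positive. This applies the rescue rule already in SAP 2.5.3.
4. Align the closing formula with the revised bullets.

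The samples and EIA results are already scheduled, and no change to treatment timing is proposed. The cost is a few lines of SAP text, a check on whether nitazoxanide times are available, and a slightly less favourable curve where a resolution becomes a censored time.

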8.1 Screening

It is permissible to re-screen a participant once if s/he fails the initial Screening (see Section 5.1). Participants need to re-consented (see Section 7) for re-screening and a new participant number must be assigned (see Section 6.3).

In the case where a safety laboratory assessment at Screening and/or Baseline is outside of the range specified in the eligibility criteria (see Section 5.2), the assessment may be repeated once. If the repeat value remains outside of the specified ranges, the participant must be excluded from the study.

8.1.1 Eligibility screening

Results of below screening measurements will be available as source data at the study site and will not be recorded within the eCRF unless specified below.

8.1.1.1 Hepatitis screen, HIV screen

All participants will be screened for Hepatitis B surface antigen (HBsAg) and, if standard local practice, Hepatitis B core antigen (HBcAg). Screening for Hepatitis C will be based in HCV antibodies and if positive, HCV RNA levels should be determined.

Evaluation for HIV seropositivity will be performed, and, if positive, confirmed by a second technique available at the laboratory site or a central lab e.g. Western blot. Appropriate counseling will be made available by the Investigator in the event of a positive confirmatory test. Notification of state and federal authorities, as required by law, will be the responsibility of the Investigator.

8.1.1.2 Alcohol test, Drug screen, Urine cotinine

Participants will be tested for evidence of alcohol and substances of abuse (e.g. alcohol, amphetamines, barbiturates, benzodiazepines, cannabinoids including tetrahydrocannabinol (THC), cocaine and opiates). Each participant will be tested for urine cotinine levels.

8.1.1.3 Understanding of Cryptosporidium Infection & Transmission Quiz

Participants will be educated on facts about *Cryptosporidium* disease, safety measures and transmission risks. They must then score 100% on a quiz assessing their understanding of *Cryptosporidium* infection and transmission. Participants will have the opportunity to retake the quiz.

8.1.1.4 SARS CoV-2 Screen

As applicable by local guidelines and regulations, participants will undergo testing of SARS CoV-2 infection to be allowed to participate in the study. COVID-19 prevention policies will be followed. SARS CoV-2 screen results will be entered into the database.

8.1.2 Information to be collected on screening failures

Participants who sign an Informed Consent form and subsequently found to be ineligible will be considered a screen failure. The reason for screen failure should be entered on the applicable

Case Report Form. The demographic information, informed consent, and Inclusion/Exclusion pages must also be completed for screen failure participants. No other data will be entered into the clinical database for participants who are screen failures, unless the participant experienced a serious adverse event during the screening phase (see Section 10.1.3).

Participants who sign an Informed Consent and are considered eligible but fail to receive a dose of ABO809 for any reason will be considered an early terminator. The reason for early termination should be captured on the appropriate disposition Case Report Form.

8.2 Participant demographics/other baseline characteristics

Participant demographics including full date (only if required and permitted) or year of birth or age, sex, race/predominant ethnicity (if permitted) and relevant medical history/current medical conditions (until date of signature of informed consent) will be recorded in the eCRF. Where possible, the diagnosis and not symptoms should be recorded. Participant race/ethnicity data are collected and analyzed to identify any differences in the safety and/or efficacy profile of the treatment due to these characteristics. In addition, the diversity of the study population will be assessed as required by Health Authorities.

All prescription medications, over-the-counter drugs and significant non-drug therapies prior to the start of the study must be documented. See Section 6.2.1 (Concomitant Therapy) for further details on what information must be recorded on the appropriate page of the eCRF.

